All eligible adult volunteers will be enrolled regardless of their baseline 25(OH)D level as it is important in this non-inferiority study to show there is no potential for harm from phototherapy, even if the baseline 25(OH)D level is above 30 ng/mL. If the goal is to develop a self-care kiosk, individuals will not have the ability to check their serum vitamin D status prior to use. We also want to learn the trajectory of vitamin D absorption and availability over a 3-4-month period in order to make evidence-based therapeutic recommendations. It is not possible to blind the subjects or research team to the group assignment given the two comparators.

Serum levels of 25(OH)D, calcium, and parathyroid hormone are drawn at baseline (T0), immediately following the intervention at 10 weeks (T6); at 14 weeks (T8), 25(OH)D is drawn to document sustainment of treatment effect. Remuneration in the form of \$20 Amazon gift cards is provided to all volunteers after the baseline and final scheduled blood draw (as allowed by DoD Instruction 3216.02 Dated November 8, 2011).

A survey shall be completed at T1 and reviewed with participants again at the 10-week visit to capture relevant demographic, medical history, sun exposure, travel, daily activities, and dietary data. Active duty SMs shall report the number of days on profile (activity restriction) for the previous three months, at T1 and T6. A Device Usability Scale will be administered to the kiosk group participants upon protocol completion to address acceptability and feasibility of the treatment. With the assistance of a biostatistician, we will analyze data using repeated measures analysis of variance adjusting for significant covariates such as 25(OH)D level at baseline. Logistic regression analyses are used to predict outcomes and explain the interrelationships among variables, i.e. age, gender, BMI, body fat, ethnicity, and sun exposure relationship to 25(OH)D serum levels.

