6.2 Discussion of the Study Design, Including the Choice of Control Groups

The objective of this non-inferiority study is to demonstrate the ability of the phototherapy kiosk to safely administer UVB radiation to participants with sufficient or insufficient levels of 25(OH)D and achieve comparable levels of serum 25(OH)D in a similar population of adults randomized to receive the RDA of 600 IU vitamin D oral supplementation once daily. As an experimental device, it is important to evaluate its equivalence to standard of care in the maintenance of sufficient levels of vitamin D in adults with all skin types between 18 and 69 years of age. In this study the supplement group (CG) was used as an active control.

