6.3.3 Removal of Patients from Therapy or Assessment

Participants enrolled in the study are free to withdraw at any time without repercussions; the study team requested to be informed in writing of their decision to withdraw.

Volunteers are reminded that the Principal Investigator of the research study may terminate their participation in the research study at any time if she determined this to be in their best interest, if they are unable to comply with the procedures required, or if they no longer meet eligibility criteria.

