6.4.4 Selection of Doses in the Study

Comparison Group - Oral Supplement Dosing

For this non-inferiority study, the logical choice for a comparison arm was the Recommended Daily Allowance (RDA) of 600 IU vitamin D for adults in the age range of 18-70 years old. The RDA was established by the Institute of Medicine (IOM) who identified clinically significant levels of circulating 25(OH)D (20 ng/mL) and then estimated the amount of dietary vitamin D required to reach this circulating level with minimal sunlight exposure. The RDA for vitamin D represents a daily intake sufficient to maintain bone health and normal calcium metabolism in 97.5% the population.²⁰

Treatment Group - Phototherapy Dosing

All patients shall be dosed at 0.6 MED at a distance of 12" from the light source for all treatments. This is consistent with dosing demonstrated to be effective at raising serum 25(OH)D without the risk of adverse events.^{26, 27} Treatments shall occur on a 14-day interval (+/- 24 hours), for a total delivery of 6 doses.

To obtain dose, each participant will self-assess their skin type according to the Fitzpatrick skin typing scale using software inside the kiosk. The kiosk will determine the dose per patient, based on their answers. Erythema response to the previous treatment dose is self-assessed. In the event erythema is self-reported via the kiosk, the participant's dose is reduced by the system for subsequent treatments.

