6.4.5 Selection and Timing of Dose for Each Patient

Comparison Group

Each participant assigned to the comparison group will be instructed to take one vitamin D3 pill each day with a meal for 70 days. Participants will also be instructed not to take any additional vitamin D supplementation during the study period. This dosing frequency is consistent with the RDA recommendation.²⁰

Treatment Group

Treatments shall occur on a 14-day interval (+/- 24 hours), for a total delivery of 6 doses. Each participant is informed of the need for consistency in the time of day for subsequent phototherapy treatments and every attempt will be made to ensure the participants return 14 days after each treatment for 10 weeks. This dosing frequency is consistent with the minimum recommended for Solius vitamin D therapy previously shown to be adequate in maintaining serum 25(OH)D levels.^{26, 27}

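### The plan has a safety objective but no adverse-event question or safety analysis in either arm; kiosk-reported erythema covers one arm and, apparently, at most five of six doses

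*Combined protocol and SAP*

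**What the plan says.** Section 6.2 says the trial is meant to "demonstrate the ability of the phototherapy kiosk to safely administer UVB radiation to participants with sufficient or insufficient levels of 25(OH)D". Section 6.1 gives the reason for enrolling people at any baseline level as the need to "show there is no potential for harm from phototherapy, even if the baseline 25(OH)D level is above 30 ng/mL".

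The plan describes these sources of harm information:

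- **Laboratory, both arms.** 25(OH)D, calcium and parathyroid hormone at baseline and 10 weeks, and 25(OH)D again four weeks later (section 6.1). An Endocrine consultant reviews abnormal values (section 6.5.1).
- **Erythema, phototherapy arm only.** Section 6.4.4: "Erythema response to the previous treatment dose is self-assessed. In the event erythema is self-reported via the kiosk", the system reduces that participant's later doses.
- **General health information.** The survey, which includes medical history, is gone over again at 10 weeks, and active-duty members report days on activity restriction (section 6.1). Neither is designated as harm data.
- **Attrition.** Tracked by arm (section 6.5.1), with no mention of recording the reason.

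On timing, section 6.4.5 states: "Treatments shall occur on a 14-day interval (+/- 24 hours), for a total delivery of 6 doses". Table 1 marks Time 6 as the final exposure. Time 7, the last blood draw, comes four weeks after it. On oversight, exposures are supervised (section 6.1), and under section 6.3.3 the Principal Investigator "may terminate their participation in the research study at any time if she determined this to be in their best interest".

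**The concern.** Section 6.5 carries safety in its title, but it defines no adverse event, severity grade or reporting route. Table 1 has no adverse-event row. The analysis plan in section 6.6.1 names only serum vitamin D. A team following the plan exactly would end the trial with laboratory values in both arms and a partial erythema record in one.

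The device is at a premarket stage and is intended for self-care, so readers will look for a statement about skin, eye and general tolerability. The plan gives no denominator, no comparator and no table for such a statement. Erythema reports also steer later dosing, so a missed report affects the exposure that follows as well as the record.

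**Working it through.** **1. Number of exposures.** Table 1 puts exposures at weeks 1, 3, 5, 7, 9 and 11 after the initial visit. That is 10/2 + 1 = 6, which reproduces the plan's six doses.

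**2. Recall interval (inferred).** Section 6.4.4 says the report concerns the previous dose and is made via the kiosk. Sessions are 14 days apart, give or take 24 hours. If the question is put at the next session, recall runs from 14 − 1 = 13 to 14 + 1 = 15 days. The time of asking is not stated.

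**3. Coverage.** Six exposures have five following sessions. Dose 6 is given at Time 6 and no kiosk session comes after it. At most 5/6 = 83% of doses can have an erythema report, even with perfect attendance and recall.

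**4. Objective against measurement.**

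| Type of harm | Phototherapy arm | Supplement arm | Analysis named in 6.6.1 |
|---|---|---|---|
| Biochemical | Laboratory values, Endocrine review | Same | 25(OH)D only |
| Erythema | Kiosk self-report, doses 1 to 5 | Not asked | None |
| Other skin, eye, general clinical | No specific question | No specific question | None |

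The Device Usability Scale does not fill the gap: it goes to the kiosk arm only and covers cleanliness, ease of use and comfort.

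**5. Early leavers.** Section 6.6.1 limits the analysis to people with a valid baseline and one or more later draws, and the first later draw is at Time 6. Someone who leaves before then because of a reaction would be counted as attrition. Nothing planned would record why, unless they had already reported erythema at the kiosk.

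**6. The dose statements.** Section 6.4.4 first fixes every treatment at 0.6 MED and then has the system lower the dose after reported erythema. Read literally, both cannot hold for a participant who reports erythema. An erythema rate pooled over sessions would then mix doses.

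**7. Precision with complete capture.** Assume 1:1 allocation, which is not stated. The planned totals of 60, 78 (= 60 × 1.30) and 120 give 30, 39 and 60 phototherapy participants. With zero events, the one-sided 95% upper bound is 1 − 0.05^(1/n):

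- n = 30: 9.5%
- n = 39: 7.4%
- n = 60: 4.9%

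With 30 participants and a true rate of 2%, the chance of seeing at least one event is 1 − 0.98^30 = 0.45. Even complete collection would exclude only fairly common harms, so there is little room to lose reports.

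**The case against.** Four counter-arguments deserve weight.

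- **Silence is not absence.** Exposures are supervised, the Project Director oversees phototherapy, and the Principal Investigator can end participation. Section 2.3 refers to a consent form and an IRB-approved protocol held separately, and these may contain event-reporting rules. A reader might infer that no clinician would ever hear of a reaction. The documents do not support that; they show only that no notification is described.
- **Other data could reveal harm.** A reader might also infer that erythema is the only harm collected outside the laboratory. The 10-week survey review and the days on activity restriction could pick up health changes. Erythema is the only *specific* non-laboratory harm named.
- **The safety objective is partly served.** Section 6.1 ties its harm concern to baseline 25(OH)D above 30 ng/mL, which is largely a biochemical question. It has two-arm data and specialist review. Safety is also not one of the three aims in section 5. To say that the objective cannot be answered would therefore go too far.
- **The timing is inferred.** Section 6.4.2 mentions cloud-based software. If participants could report from outside the kiosk, recall would be shorter and dose 6 could be covered. No such route is described.

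It can also be said that the dose statements read as a general rule with an exception. That is plausible, but the words applying 0.6 MED to every treatment still need reconciling. Finally, contacting only the kiosk arm after each exposure would add unequal attention in an unblinded trial with uncontrolled sun exposure. That objection stands, and the fix allows for it.

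None of this supplies an adverse-event question, a comparator or a safety analysis.

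**Conclusion.** The concern holds for skin, eye and other clinical safety. As written, that information is incompletely captured and cannot be compared between arms, and no analysis of it is planned. Biochemical safety is measured in both arms.

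The absence of an adverse-event question and of a safety analysis is read directly from section 6.5, Table 1 and section 6.6.1. The 13 to 15 days of recall and the limit of 5 in 6 doses rest on the inference that erythema is asked about at the next kiosk session. The upper bounds of 4.9% to 9.5% assume equal allocation.

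Delayed recall may lower the recorded erythema rate, but the documents give neither a rate nor any recall data, so the amount cannot be stated. This should be changed. It does not affect the randomization or the primary endpoint.

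**What to change.** 1. **Ask both arms the same questions.** At the existing Time 6 and Time 7 contacts, use one form with an open adverse-event question and solicited items, including skin and eye symptoms. Time 7 then covers dose 6, although with four weeks of recall. Record the reason for each withdrawal. Tabulate the results by arm, and include participants who leave before any follow-up draw.
2. **Route the kiosk reports.** Copy each erythema report to the study team, so that the Principal Investigator's judgement under section 6.3.3 has the information. Optionally, send a brief automated symptom query within days of each exposure, with a matching query to the supplement arm to keep contact equal.
3. **Reconcile section 6.4.4.** Make the statement that 0.6 MED applies throughout consistent with the statement that the dose falls after reported erythema, and report erythema by the dose actually delivered at each session.

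The cost is protocol wording and one more form at existing contacts, plus automated messages if the optional query is adopted. Prompted reporting will raise the recorded event rate, and the report should say so.

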6.4.5 Selection and Timing of Dose for Each Patient

Comparison Group

Each participant assigned to the comparison group will be instructed to take one vitamin D3 pill each day with a meal for 70 days. Participants will also be instructed not to take any additional vitamin D supplementation during the study period. This dosing frequency is consistent with the RDA recommendation.²⁰

Treatment Group

Treatments shall occur on a 14-day interval (+/- 24 hours), for a total delivery of 6 doses. Each participant is informed of the need for consistency in the time of day for subsequent phototherapy treatments and every attempt will be made to ensure the participants return 14 days after each treatment for 10 weeks. This dosing frequency is consistent with the minimum recommended for Solius vitamin D therapy previously shown to be adequate in maintaining serum 25(OH)D levels.^{26, 27}

6.4.6 Blinding

Due to the nature of the study, it is not possible to blind the subjects or research team to the group assignment.

6.4.7 Prior Concomitant Therapy

Other medications are allowed except those listed in the exclusion criteria (anti-seizure medications, cyclosporine, and idinavir). The research pharmacist will provide expertise for establishing screening criteria to eliminate any potential drug-drug or drug-nutrient interactions. No attempt will be made to control for sun exposure or dietary intake of vitamin D, however, all participants are instructed to refrain from taking any additional supplements containing vitamin D. Volunteers will be asked about vitamin D supplementation during screening and anyone taking a vitamin D supplement in the previous 2 months will not qualify for the study. Both amount of sun exposure and consumption of dietary vitamin D will be captured on surveys. Logistic regression analyses will be used to predict outcomes and explain the interrelationship among the two variables (i.e. sun exposure relationship to 25(OH)D serum levels).

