2.3 Patient Information and Consent

All patients provided written informed consent to participate in the study prior to being screened. The patient was given a copy of the signed consent form for their personal records. The original copy of the informed consent is kept in document control along with this test report. A sample of the consent form can be found along with the IRB-approved study protocol.

3 Investigators and Study Administrative Structure

The table below shows the principal study personnel involved in the study.

Title	Name and Affiliation
Principal Investigator	[name], RN, FAAN. MAMC
Sponsor	BeneSol, Inc. dba SOLIUS
Project Manager	[name], MS, RD, LD. MAMC
Clinical Research Associate(s)	[name], BSN, RN. MAMC
Biostatistician	[name], MA. (Contractor)

4 Introduction

Low vitamin D status is common in individuals who regularly perform extreme physical exertion, particularly in combination with periods of psychological stress, inadequate nutrition, and sleep disruption.¹ This places military personnel in a high risk category with significant negative consequences to musculoskeletal, immune, and mental health, and thus, resilience. The large scope of this problem demands a multi-phased approach beginning with a self-care, easy access, safe biomedical device intended to stimulate cutaneous production of vitamin D. The pilot, or demonstration phase, involved installment of a standing phototherapy kiosk in an outpatient setting where we enrolled Active Duty (AD) and retired Service Members (SM), adult beneficiaries, and DA civilians to test the acceptability and feasibility of this health promotion concept. We anticipated that the phototherapy kiosk would be an inexpensive, convenient, and effective way to maintain or raise 25(OH)D levels to sustain Warfighter and beneficiary resilience.

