6.1 Overall Study Design and Plan

This non-inferiority study used a prospective, longitudinal, randomized design with repeated measures to address vitamin D sufficiency in AD, retiree, beneficiary, and DA civilian populations. It is important and necessary to conduct this study with adult humans, military personnel in particular, to determine acceptability and feasibility of this phototherapy kiosk as an addition to existing Warfighter resources to promote health and resilience. Following Madigan Army Medical Center (MAMC) Institutional Review Board Human Subjects and Ethics approval, the SPK will be installed in a location approved by the Radiation Safety Officer, the study team will be hired, and recruitment will begin for an anticipated 12-month project period. Approximately 120 volunteers will be approached from MAMC and Joint Base Lewis-McChord (JBLM), a large joint base in the Pacific Northwest, where over 25,000 Soldiers and Airmen train every day and regional beneficiaries' number ~98,000. Recruiting efforts will attempt to capture a representative sample of the population including both genders, diverse ethnicities, and a range of age (18-70 years) and body mass index (BMI), who have no contraindication for UVB exposure or oral vitamin D supplementation. In addition to walk-in volunteers, the research team will attend the JBLM Newcomer's Orientation. Using a computer-generated block design, volunteers will be randomized to one of two groups by the research pharmacist; 1) oral vitamin D supplementation, or 2) standing phototherapy kiosk with UVB exposure, for a 10-week period.

Comparison Group (CG) – Supplement

A MAMC research pharmacist will dispense a 70-day supply of the vitamin D3 600 IU oral supplement to subjects assigned to this group. The Project Director will work with the pharmacist to coordinate pick-up of supplement bottles for subjects or optimal in-person dispensing times.

Treatment Group (TG) – Phototherapy

The Project Director provides oversight for the phototherapy treatment. The kiosk will deliver the UVB dose under supervised conditions over a 1 – 10 minute interval based on the Fitzpatrick skin type with the subject wearing minimal or no clothing, preferably no more than a bathing suit, and protective eye-wear. The experience in the SPK was designed to be comfortable and user-friendly.

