6.3.2 Exclusion Criteria

- Any volunteer with relocation, deployment, or release from active duty in the next 4 months
- Pregnant, or currently breastfeeding, females
- Anyone with chronic health problems (e.g. kidney disease, liver disease, intestinal malabsorption)
- Any volunteer currently taking vitamin D supplementation
- Taking medications for an endocrine disorder, such as Synthroid or oral hypoglycemic agents
- Sarcoidosis
- Medications having a high potential for interaction with vitamin D:
 - anti-seizure medications, cyclosporine, indinavir (Crixivan)
- Adults diagnosed with light allergies:
 - Actinic prurigo, Polymorphous light eruption, Solar urticaria
- Adults diagnosed with light sensitivities:
 - Protoporphyrinia, Photodermatitis, Xeroderma pigmentosum, Lupus erythematosus, Actinic dermatitis, UV-sensitive syndrome

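### Section 6.1 seeks volunteers with no contraindication to UVB, but no written medicine rule covers light-sensitising medicines, and the first 0.6 MED dose is adjusted for skin type only.

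*Combined protocol and SAP*

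**What the plan says.** All references are to the combined protocol and SAP.

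- **Recruitment aim (6.1).** The trial seeks a representative sample of adults "who have no contraindication for UVB exposure or oral vitamin D supplementation". UVB and oral vitamin D stand side by side in that aim.
- **Medicine exclusions (6.3.2).** There are three: current vitamin D supplements; medicines for an endocrine disorder; and "Medications having a high potential for interaction with vitamin D", given as anti-seizure medicines, cyclosporine and indinavir.
- **Light-related exclusions (6.3.2).** These apply to adults already diagnosed with one of the listed light allergies or light sensitivities. Photodermatitis is on the list. No medicine is.
- **Concomitant medicines (6.4.7).** Medicines outside the exclusion list are permitted. On screening, the section says: "The research pharmacist will provide expertise for establishing screening criteria to eliminate any potential drug-drug or drug-nutrient interactions".
- **Dosing (6.4.2 and 6.4.4).** Every kiosk participant is dosed at 0.6 of a skin-type-adjusted MED, with skin type self-assessed at the kiosk. If the participant reports erythema, the system lowers later doses.
- **Objective (6.2).** The device is to "safely administer UVB radiation to participants" whose vitamin D status may be sufficient or insufficient.

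**The concern.** The intervention in the kiosk arm is light, delivered to the whole body with little or no clothing. A medicine can therefore matter in two ways: by interacting with vitamin D, or by making the skin more sensitive to UVB. The plan writes a rule for the first and none for the second. The stated screen covers interactions with drugs and nutrients, and UVB is neither.

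The diagnosis-based exclusions do not fill the gap. They catch a person whose light reaction has already been recognised. They do not catch a person who takes a light-sensitising medicine and has not yet had a relevant exposure.

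What is at stake is participant safety at the first exposure, measured against the plan's own aim of safe administration.

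**Working it through.** No sample size, power or error rate bears on this point. The check is a comparison of the rules, plus one piece of arithmetic for scale.

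**1. The dose as stated.** Section 6.4.4 gives 0.6 MED and section 6.4.2 gives 60% of MED. The two agree.

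**2. Count of the exclusions in 6.3.2.**

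| Type | Count | Refers to UVB or light |
|---|---|---|
| Diagnosed light allergies | 3 | 3 |
| Diagnosed light sensitivities | 6 | 6 |
| Medicine exclusions (supplements, endocrine, vitamin D-interacting) | 3 | 0 |

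So 3 + 6 = 9 diagnoses address light, and 0 of 3 medicine rules do.

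**3. Following one volunteer through the rules.** Take a volunteer in good health, on a light-sensitising medicine outside the three excluded groups, with no diagnosed light condition.

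- 6.3.2: no exclusion applies.
- 6.4.7, first sentence: the medicine is allowed.
- 6.4.7, pharmacist's screen: as worded, it does not reach a drug-light interaction.
- 6.5.1: the demographic questionnaire records current medications, but no eligibility or dosing action depends on the answer.
- 6.4.4: the first dose is 0.6 MED, set from skin type. Reduction depends on erythema reported after an earlier treatment, so it cannot act on the first dose.

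Only the general wording of the 6.1 aim and the investigator's discretion in 6.3.3 stand in the way. Neither mentions medicines.

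**4. The margin, for scale only.** Let f be the proportional fall in a person's own MED caused by a medicine. The documents give no value for f, so it is an assumption, as is the premise that skin type predicts MED. The dose as a fraction of the person's actual MED is 0.6/(1 − f).

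| f | 0.6/(1 − f) |
|---|---|
| 0 | 0.60 |
| 0.10 | 0.67 |
| 0.20 | 0.75 |
| 0.30 | 0.86 |
| 0.40 | 1.00 |
| 0.50 | 1.20 |

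The margin below 1 MED is used up when f reaches 0.40. This describes the margin. It is not evidence that any participant would reach it.

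**The case against.** The strongest reply is that this argues from silence in an incomplete file. Section 6.4.7 says the pharmacist will help to establish screening criteria, and those criteria are not in the file. Nor are the consent pages. Section 2.3 says "A sample of the consent form can be found along with the IRB-approved study protocol", which suggests that the approved protocol may be a separate document. A rule on light-sensitising medicines could sit in any of these, and a pharmacist could reasonably read the 6.1 aim as covering medicines. This stands as a limit: the point concerns the rules written here. A reader might infer that no such screening took place, or that people on these medicines were exposed. The documents do not support either inference.

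Second, there are real safeguards. Volunteers must consider themselves in good health, and those with chronic health problems are excluded, which should reduce the number on long-term medicines. Diagnosed photodermatoses are excluded. The dose is below 1 MED, the investigator may end participation, and "The kiosk will deliver the UVB dose under supervised conditions". These reduce how many people are affected and how badly. None asks whether a medicine is compatible with UVB.

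Third, the documents never mention light-sensitising medicines and do not say whether any medicine lowers the erythema threshold in the device's 293–303 nm band. That is correct, and it is why the list belongs to the pharmacist and clinicians and why no risk figure is given.

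A reader might also call the first dose unadjusted. It is adjusted for skin type; what is missing is any adjustment for medicines.

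**Conclusion.** The point holds as a gap between the recruitment aim in 6.1 and the rules in 6.3.2 and 6.4.7. It is more than missing detail, because 6.4.7 positively permits medicines outside the exclusion list. Under the rules as written, a volunteer on a light-sensitising medicine without a diagnosed reaction can receive a first full-body dose of 0.6 MED that takes no account of the medicine.

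The size of the risk is unknown. The documents do not show how many volunteers take such a medicine, how far their threshold falls, or how many would react. The 40% figure rests on an assumed fall in MED and on skin type predicting MED, and should not be read as a forecast of burns.

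A reader might also infer that the non-inferiority comparison of 25(OH)D is compromised. Nothing in the documents shows that, and it is not claimed.

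The change should be made because it is cheap and concerns safety. The title page gives a completion date in 2019, so its practical use is in text carried into later phases, particularly given the self-care use described in 6.1.

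**What to change.** 1. **Section 6.3.2:** add an exclusion for medicines that the research pharmacist and clinicians judge to be light-sensitising in the UVB band.
2. **Section 6.4.7:** add that class to the bracketed list of excluded medicines, and extend the pharmacist's screen to drug-drug, drug-nutrient or drug-UVB interactions. Changing the screening sentence alone would leave the first sentence of 6.4.7, and 6.3.2, at odds with it.
3. **Timing:** apply the screen at the Initial visit, before randomisation. Section 6.3 requires identical criteria in both groups; a check made only in the kiosk arm after assignment would remove people from one arm.
4. **During treatment:** ask kiosk participants about new medicines before each exposure. If one is reported, the pharmacist clears it first. The participant stays in follow-up and is analysed in the assigned arm, whether or not that exposure goes ahead.

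**Cost.** Two edits to the text, a longer pharmacist checklist, and one question at each of 6 exposures. With equal arms (an assumption) and totals of 60, 78 or 120, that is 6 × 30 = 180, 6 × 39 = 234 or 6 × 60 = 360 questions. There will also be a small number of pharmacist clearances. A few volunteers become ineligible, and an occasional exposure may miss its window of 14 days ± 24 hours.
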